6.2 SAFETY POPULATION

The Safety Population will consist of all participants who received at least 1 administration of study treatment.

7.0 PATIENT DISPOSITION

Participant disposition encompasses the distribution of participants screened, randomized, treated, and who completed or discontinued the study (along with reasons for withdrawal/discontinuation). Participant disposition will be summarized for all screened participants in total and by treatment group.

8.0 DEMOGRAPHICS AND OTHER BASELINE CHARACTERISTICS

8.1 DEMOGRAPHICS AND BASELINE CHARACTERISTICS

Demographic parameters (age; age group; sex; race; ethnicity), baseline characteristics (weight; height; body mass index, calculated as weight [kg]/(height [m])²; Fitzpatrick skin phototype [Table 8-1], baseline PASI, % Body Surface Area (BSA), and PGA) will be summarized descriptively for the mITT Population by treatment group and in total. Continuous variables will be summarized by number of participants and mean, SD, median, minimum, and maximum values. Categorical variables will be summarized by number and percentage of participants.

Table 8-1 **Fitzpatrick Skin Phototype**

Type	Description
I	Always burns easily; never tans (sensitive)
II	Always burns easily; tans minimally (sensitive)
III	Burns moderately; tans gradually (light brown) (normal)
IV	Burns minimally; always tans well (moderate brown) (normal)
V	Rarely burns; tans profusely (dark brown) (insensitive)
VI	Never burns; deeply pigmented (insensitive)

Source: Federal Register 1999

8.2 MEDICAL HISTORY

Medical history, encompassing abnormalities and surgeries reported as occurring before Day 1, will be coded using the Medical Dictionary for Regulatory Activities (MedDRA), version 20.1 or newer. Unique participants who report medical history events will be summarized by MedDRA system organ class (SOC) and preferred term (PT) for the mITT Population by treatment group. Medical history will be summarized separately for those ongoing at Day 1 and those not ongoing at Day 1.

8.3 PRIOR AND CONCOMITANT MEDICATIONS

Medications will be coded using the World Health Organization (WHO) Drug Dictionary. Prior medications are medications taken ≥ 1 time before the study treatment start date, regardless of medication end date. Concomitant medications are medications taken ≥ 1 time on or after the study treatment start date, regardless of medication start date. Unique participants who reported medications will be summarized by WHO Drug class and preferred drug name for the mITT Population by treatment group. Prior and concomitant medications will be summarized separately.

9.0 EXTENT OF EXPOSURE AND TREATMENT COMPLIANCE

9.1 EXTENT OF EXPOSURE

Exposure to the investigational product for the Safety Population during the double-blind treatment period will be summarized in terms of treatment duration, calculated as the number of days from the date of the first dose of double-blind investigational product to the date of the last dose of double-blind investigational product during the double-blind treatment period, inclusive. Descriptive statistics (number of participants, mean, SD, median, minimum, and maximum) will be presented by treatment group.

Patient-years, defined as total exposure to double-blind investigational product in years will be summarized by treatment group for the Safety Population.

9.2 MEASUREMENT OF TREATMENT COMPLIANCE

Dosing compliance for the study period is defined as the total number of capsules (Row 1 + Row 2) actually taken by a participant during the study (from first treatment start date until the last treatment end date) divided by the number of capsules prescribed (2 capsules a day) for the same period multiplied by 100. If the total number of capsules for any week is missing, that week will be excluded from the compliance calculation. This information will be obtained from study treatment record of the participant's eCRF.

Descriptive statistics for study drug compliance will be presented by treatment group for the whole double-blind treatment period, for the Safety Population.

10.0 EFFICACY ANALYSES

The efficacy analyses will be based on the mITT Population, defined as randomized participants with at least 1 postbaseline PASI assessment. *Baseline* for efficacy is defined as the last non-missing efficacy assessment before the first dose of study treatment. All efficacy analyses will be conducted using observed data. All statistical tests will be 2-sided hypothesis tests performed at the 5% level of significance for main effects. All confidence intervals will be 2-sided 95% confidence intervals, unless stated otherwise.

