**Number of Participants:**

Participants will be screened to achieve approximately 200 randomly assigned to study medication and an estimated total of 160 evaluable participants who will complete the study (estimated 40 evaluable participants per treatment group).

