## 5. Study Design

### 5.1. Overall Design

This is a double-blind, randomized, placebo-controlled trial to evaluate the efficacy, safety, tolerability, pharmacokinetics and pharmacodynamics of AGN-242428 when administered once-daily for 16 weeks to adults with moderate to severe plaque psoriasis. The study consists of 3 periods, as described below. Details of individual assessments to be completed at each study visit are included in Section 2.

**Screening Period:** The purpose of the screening period is to evaluate potential study participants and to qualify them for enrollment into the study. This period begins at the point of informed consent and ends when the participant is randomized to treatment. The screening period will be up to 4 weeks ( $\leq$  28 days) in duration.

**Treatment Period:** Participation in the study begins at the point the participant is randomized. The treatment starts after his/her first dose of study medication and ends after 16 weeks of treatment or at the point of permanent study medication withdrawal should the participant discontinue treatment prior to completion of Week 16.

On Day 1 of the treatment period, qualified participants will be randomly assigned to receive 16 weeks of once-daily oral treatment with [REDACTED] AGN-242428, [REDACTED] AGN-242428, [REDACTED] AGN-242428, or placebo. Baseline data for evaluation of participant efficacy and safety will be obtained on Day 1, prior to receiving the first dose. Participants will complete study visits on the first day of treatment and following 2, 4, 6, 8, 10, 12 and 16 weeks of treatment for evaluation of efficacy safety and tolerability assessments.

A subset of approximately 14 to 18 participants in each treatment group (includes placebo), who have provided consent, will have sequential blood samples collected at scheduled times before and up to 24 hours after study medication administration during the Week 4 visit to establish AGN-242428 PK concentration versus time profiles. All participants will have blood samples collected to determine trough AGN-242428 concentrations obtained on Day 1 and at the Week 4, 8, 12 and 16/early termination visits. Random time PK sampling at Weeks 6 and 10 (in addition to other assessments eg, select laboratory tests [see Table 9-4] and AEs [Section 9.2]) will also be obtained in all participants.

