## 8. Discontinuation/Withdrawal Criteria

Withdrawn participants are those who do not complete all evaluations and procedures outlined in the protocol. Participants who discontinue taking study medication for any reason must also be withdrawn from the study. All AEs that are present when the participant withdraws from the study will be followed as described in Section 9.2.

Participants may voluntarily withdraw from the study at any time.

Notification of early participant discontinuation from the study and the reason for discontinuation will be made to the sponsor and will be clearly documented on the appropriate eCRF.

Reasons for discontinuation from the study treatment and/or the study may include the following:

- AE
- Death
- Lost to follow-up
- Non-compliance with study drug
- Meets study defined stopping criteria
- Investigator decision
- Pregnancy
- Protocol deviation
- Screen failure
- Site terminated by sponsor
- Study terminated by sponsor
- Withdrawal by subject
- Completed
- Other

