## 9.5. Pharmacokinetics

Blood samples for the analysis of AGN-242428 plasma concentrations will be collected at scheduled times (Section 2). Instructions for the collection and handling of biological samples will be provided by the central laboratory. The actual date and time (24-hour clock time) of each sample will be recorded. Trough and random PK blood samples will be drawn from all participants; sequential PK samples will be drawn in a subset of participants. The participants will be asked to provide the date and time of administration of the 3 doses taken prior to the visit when PK samples are to be drawn. This date and time information will be recorded in the eCRF.

**Trough PK samples:** Trough PK samples will be collected from all study participants. Samples that are designated as trough (Day 1 and Weeks 4, 8, 12 and 16) will be collected before on-site administration of the morning dose of study medication. In case of early termination, a blood sample for AGN-242428 plasma concentration will be drawn at the early termination visit. The date and time of PK sample collection will be recorded in the eCRF. Deviations to sample collection such as failure to collect the sample, collection of the sample after dose administration, or deviations to dose administration in the 3 days prior to sample collection will be recorded in the eCRF.

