## 10. Statistical Considerations

### 10.1. Sample Size Determination

A responder is a participant with  $\geq 75\%$  reduction in PASI from baseline to Week 16. The sample size of 200 participants (50 per treatment arm) will provide 90% power to detect a response rate difference of 27% between each AGN-242428 and placebo group at Week 16, with an assumed response rate of 6% in the placebo group, a 5% type 1 error rate, and 20% dropout rate.

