### 10.2. Populations for Analyses

The analysis populations will consist of participants as defined in [Table 10-1](#).

**Table 10-1** Analysis Populations

Population	Definition	Study Treatment
Modified intent-to-treat (mITT)	All randomized participants with at least 1 postbaseline PASI assessment. This population will be used for all efficacy analysis.	Randomized assignment
Pharmacokinetic (PK)	All participants who received AGN-242428 and had available plasma concentration data. The PK analysis set will be used for all PK analyses.	Actual received
Pharmacodynamic (PD)	All participants for whom PD measurements are available at baseline and at least one postbaseline visit.	Actual received
Safety	All participants who received $\geq 1$ administration of study treatment.	Actual received

PASI = Psoriasis Area and Severity Index

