16.0 DATA HANDLING CONVENTIONS

If the assessment date is on or after the date of the first dose of study treatment, the study day is calculated by assessment date – date of the first dose of study treatment + 1. If the assessment date is before the date of the first dose of study treatment, the study day is calculated by assessment date – date of the first dose of study treatment. Therefore, a negative day indicates a day before the start of the study treatment. If the assessment date is unavailable, use the visit date instead.

If a participant has 2 or more visits within the same window, the last visit with a nonmissing value will be used for analysis.

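### The Week 16 responder tests use observed data, with no visible rule for participants who have no Week 16 score; if stopping differs by arm, the primary comparison is biased.

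*SAP*

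**What the plan says.** SAP 10.0 sets one data rule for efficacy: "All efficacy analyses will be conducted using observed data". It governs the chi-square test of PASI 75 at Week 16 (SAP 10.1) and the chi-square tests of PASI 50, PASI 90 and the two PGA responder endpoints (SAP 10.2).

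The efficacy set is the mITT population. Protocol 10.2 says of it, "This population will be used for all efficacy analysis". Membership needs only one postbaseline PASI, so a participant can be in mITT with no Week 16 value.

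Protocol Section 8 says: "Participants who discontinue taking study medication for any reason must also be withdrawn from the study". Protocol Appendix 6 keeps participants who meet a liver stopping rule in the study, but only for follow-up assessments that the protocol specifies. Protocol 10.1 plans with "a 5% type 1 error rate, and 20% dropout rate", and the synopsis expects an "estimated total of 160 evaluable participants who will complete the study (estimated 40 evaluable participants per treatment group").

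Protocol 10.3 leaves missing-data procedures to the SAP. The visible SAP has such rules for adverse event severity, causality and dates, medication dates, laboratory character values and compliance weeks, but none for efficacy. The nearest text is in SAP 16.0: "If a participant has 2 or more visits within the same window, the last visit with a nonmissing value will be used for analysis". It covers a visit window with several values, not an empty one.

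**The concern.** Taken together, these rules mean that a participant who stops early normally has no Week 16 PASI or PGA, and an observed-data analysis then leaves that participant out of numerator and denominator. The test compares responders among those who stayed, and staying can depend on treatment.

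Unequal stopping is possible here. Protocol 5.5 reports transaminase elevations at one earlier dose and not at another, and Table 8-1 stops treatment for transaminase rises. Conversely, the protocol supplies no rescue medication and bars other psoriasis therapy (7.7.3, 7.7.4), which could drive placebo participants out. More stopping on active would favour active in an observed-data test, and more stopping on placebo would favour placebo. The visible plan has no second analysis to show how far the result depends on this choice.

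**Working it through.** **Inputs from the documents.** 50 randomised per arm, 40 evaluable, 20% dropout, placebo response 6%, difference 27 points (so 33% on active), two-sided 5%, chi-square test.

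**Assumptions.** Dropout of 30% v 10%, 10% v 30% and 40% v 10% (active v placebo); response among stoppers, s, of 0 or 10% in both arms; true null rates of 6% and 20%; every randomised participant has a postbaseline PASI, so mITT N is 50 per arm. Dropout counts are held fixed.

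**Method.** Exact power or size: sum the binomial probabilities over all tables in which the uncorrected chi-square exceeds 3.841.

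**1. The plan's figure.** 40 v 40 at 33% v 6% gives 90.4%, which agrees with the stated 90%.

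**2. Power under each handling rule.** With non-responder counting, each rate becomes (1 − dropout) × the rate among those observed, on 50 per arm.

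| Dropout, active v placebo | Observed data | Power | Non-responder rates | Power |
|---|---|---|---|---|
| 20% v 20% | 40 v 40 | 90.4% | 26.4% v 4.8% | 89.6% |
| 30% v 10% | 35 v 45 | 91.3% | 23.1% v 5.4% | 76.6% |
| 10% v 30% | 45 v 35 | 88.9% | 29.7% v 4.2% | 96.3% |

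**3. Size when all-randomised rates are equal.** If the true rate is r and no stopper responds, the observed rate in an arm is r / (1 − dropout). At 30% v 10%:

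- r = 6%: 0.06/0.70 = 8.6% v 0.06/0.90 = 6.7%, with 35 v 45 observed. The test rejects 7.0% of the time, 6.0% in favour of active.
- r = 20%: 28.6% v 22.2%. The test rejects 10.7% of the time, 10.3% in favour of active.

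The nominal figure for one direction is 2.5%. At 40% v 10% the totals are 7.9% and 19.0%. At 10% v 30% they are again 7.0% and 10.7%, now mostly in favour of placebo. Non-responder counting on 50 per arm gives 4.5% and 5.2%. At equal 20% dropout the observed-data test holds its size: 5.7% and 5.0%.

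**4. One set of data, two rules.** 10/35 v 4/45 gives p = 0.022. The same responders as 10/50 v 4/50 give p = 0.084.

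**5. All-randomised difference when the observed difference is 27 points.** Difference = (1 − dA) × 0.33 + dA × s − (1 − dP) × 0.06 − dP × s, where dA and dP are dropout on active and placebo.

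| Dropout, active v placebo | s = 0 | s = 10% |
|---|---|---|
| 20% v 20% | 21.6 | 21.6 |
| 30% v 10% | 17.7 | 19.7 |
| 10% v 30% | 25.5 | 23.5 |

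**The case against.** The strongest reply has four parts.

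**The denominator is open.** Efficacy is tied to mITT, so observed responders over mITT N is a possible, though less usual, reading, and it comes close to the fix. This stands as a reason to state the denominator.

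**Hidden text may deal with it.** SAP Section 12, SAP 16.1 and the schedule of activities are not visible. The protocol does describe an early termination visit: trough samples are "obtained on Day 1 and at the Week 4, 8, 12 and 16/early termination visits", and "a blood sample for AGN-242428 plasma concentration will be drawn at the early termination visit". Whether PASI and PGA are taken there, or mapped to Week 16, cannot be checked. So one may say only that no second analysis is visible, not that none exists. The SAP 10.0 sentence covers every efficacy analysis, which makes a hidden imputation rule less likely. Mapping would bring a score from before Week 16 into a Week 16 endpoint.

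**Unequal dropout is not documented.** Only the 20% rate is in the documents. Protocol 5.5 also says that one selected dose had no liver signal, and that modelling makes rises above 3 times the upper limit of normal unlikely for most participants at another. This stands: neither the size nor the direction of any imbalance is known.

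**This is a Phase 2b trial with an openly stated rule.** That lowers the stakes, but the Week 16 contrast still answers the trial's main efficacy question. Disposition with reasons by arm (SAP 7.0) and response counts by visit (SAP 10.1, 10.2) would let a reader see unequal dropout, but they do not correct the test.

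A reader might also infer that the stated 90% power proves a completers-only analysis, since 50 v 50 without dropout gives 95.7%. It does not: non-responder counting at 20% dropout gives 89.6%, which also rounds to 90%.

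**Conclusion.** The point holds as a should-fix, with moderate confidence. On the usual reading of the stated rule, early stoppers leave the Week 16 tests. At the one documented dropout rate, taken as equal across arms, the test is essentially unaffected. Under unequal stopping in either direction the comparison is biased: at an assumed 30% v 10% with no response among stoppers, size rises to between 7.0% and 10.7%.

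Two stronger conclusions are tempting and not supported. The plan cannot be said to favour AGN-242428, because the direction depends on which arm loses more participants. Nor does the move from 27 to 21.6 points at equal dropout show bias: it is a change of estimand, from those who stayed to all randomised with stoppers as failures. The sample-size statement is not in error.

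**What to change.** In SAP 10.0 to 10.2, for the primary and secondary Week 16 responder tests:

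- count mITT participants without an on-treatment Week 16 PASI or PGA as non-responders, with mITT N as the denominator;
- state that early-termination values are not carried to Week 16;
- keep the observed-data analysis as a sensitivity analysis.

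At minimum, leave the observed-data analysis as primary, state its denominator, and prespecify the non-responder analysis as a sensitivity analysis.

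The cost is two or three sentences and one extra table, with no new visits or data. There are two downsides. Power falls if active participants stop more often (76.6% against 91.3% at 30% v 10%). If placebo participants stop more often and some stoppers would have responded, the rule slightly overstates the effect: 25.5 against 23.5 points at 10% v 30% with 10% of stoppers responding. Reporting both analyses shows how much either matters.

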10.1 PRIMARY EFFICACY PARAMETER

The primary efficacy endpoint will be percentage of participants achieving a reduction (improvement) in PASI score of $\geq 75\%$ from baseline to Week 16.

The null hypothesis is that the population responder rates of the AGN-242428 and placebo groups are the same. The alternative hypothesis is that the rates differ:

- $H_0: r_v = r_p$
- $H_a: r_v \neq r_p$

where r_v and r_p are the population rates in the AGN-242428 and placebo groups, respectively.

Frequency counts of participants achieving a $\geq 75\%$ reduction in PASI score relative to baseline will be tabulated by treatment at each postbaseline visit. The difference between each of the AGN-242428 groups and placebo in the proportion of participants with a reduction in PASI of $\geq 75\%$ from baseline, will be analyzed using a Chi-Square test.

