#### 5.4. Scientific Rationale for Study Design

This study is designed to address the following main questions:

1. Is AGN-242428 efficacious, relative to placebo, in treating participants with moderate to severe plaque psoriasis after 16 weeks of treatment?
2. Is AGN-242428 generally safe and well tolerated with long-term dosing?

**Participant selection:** Entry criteria are designed to select a population that is representative of participants with moderate to severe plaque psoriasis. Prohibited medications and diseases that may interact with AGN-242428 are excluded. Participants who have failed treatment for psoriasis with biologics targeting IL-17 and IL-23 are also excluded from the study.

**Trial design:** A randomized, double-blind, placebo-controlled design is used to reduce bias in the estimation of treatment effects. Participants are informed of the probability of being randomized to placebo and they may discontinue the trial at any time they choose.

Efficacy and safety assessments are standardized and performed regularly throughout the 16-week treatment period. Clearly defined processes for evaluation and follow-up of hepatic enzyme elevations and signs and symptoms of hepatic impairment are also included to enhance safety monitoring in the study.

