14.0 DETERMINATION OF SAMPLE SIZE

A responder is a participant with $\geq 75\%$ reduction in PASI from baseline to Week 16. The sample size of 200 participants (50 per treatment arm) was selected to provide 90% power to detect a response rate difference of 27% between each AGN-242428 and placebo group at Week 16, with an assumed response rate of 6% in the placebo group, a 5% type 1 error rate, and 20% dropout rate.

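### Do three dose-versus-placebo tests at 5% each, without a multiplicity adjustment, undermine the primary analysis?

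*SAP*

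**What the plan says.** SAP section 10.1 states the primary null in general terms: "The null hypothesis is that the population responder rates of the AGN-242428 and placebo groups are the same". The active rate carries no dose index. The section then specifies three pairwise tests: "The difference between each of the AGN-242428 groups and placebo in the proportion of participants with a reduction in PASI of" at least 75% "from baseline, will be analyzed using a Chi-Square test". Protocol section 10.3.2.1 has the same null and the same three tests, and ties the test sentence explicitly to Week 16.

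The level comes from SAP section 10.0: "All statistical tests will be 2-sided hypothesis tests performed at the 5% level of significance for main effects".

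Protocol section 5.4 puts the efficacy question for the drug as a whole: "Is AGN-242428 efficacious, relative to placebo, in treating participants with moderate to severe plaque psoriasis after 16 weeks of treatment".

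The sample-size text is written per comparison. Protocol section 10.1 gives 90% power for a 27-point difference "between each AGN-242428 and placebo group at Week 16". SAP section 14.0 repeats it, "between each AGN-242428 and placebo group at Week 16, with an assumed response rate of 6% in the placebo group", and adds "a 5% type 1 error rate, and 20% dropout rate".

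The visible text of neither document names a multiplicity procedure, a primary dose, an order of testing or a number of doses that must succeed. Neither table of contents lists a section on multiplicity.

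**The concern.** One null and one question about AGN-242428 suggest one test with one 5% error rate. The plan instead allows three chances to reject. A reader who takes 5% as the error rate for the single written null would understate it by more than half when all three doses are inert.

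The second worry is a split result. If one dose of three reaches p<0.05, nothing says whether the primary question has been answered, so the reading might be chosen after unblinding. At stake would be a positive headline resting on the best of three tests. An adjustment such as Hochberg, or a declared success rule, looks like the natural remedy.

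**Working it through.** **Inputs.** Three doses and placebo, 1:1:1:1, 50 randomized per arm (SAP section 4.0); about 40 evaluable per arm (Protocol section 5.2; 50 × 0.8 = 40); placebo response 6%, so 6% + 27% = 33% on active (SAP section 14.0); two-sided 5% per test (SAP section 10.0). The chi-square is taken without continuity correction, which the documents do not specify.

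**1. Reproduce the stated power.** With unpooled variance and 40 per arm:

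- SE = √[(0.06×0.94 + 0.33×0.67)/40] = 0.0833
- power = Φ(0.27/0.0833 − 1.96) = Φ(3.24 − 1.96) = 90.0%

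Exact enumeration of the uncorrected chi-square gives 90.4%. At the Bonferroni level of 0.05/3 the exact figure is 78.7%, and with a continuity correction 82.0%. The planned 90% is therefore a per-dose figure at an unadjusted 5%.

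**2. Overall error if no dose differs from placebo.** With equal arms sharing one placebo group, any two test statistics have correlation (1/n)/(2/n) = 0.5. With c = 1.96 and ρ = 0.5,

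P(at least one rejection) = 1 − ∫ φ(u) {Φ[(c+√ρ·u)/√(1−ρ)] − Φ[(−c+√ρ·u)/√(1−ρ)]}³ du = 12.5%.

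Counting only rejections in favour of AGN-242428 gives 6.3%.

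The exact version sums over the placebo count x: Σ Bin(x; n, p)·{1 − [1 − r(x)]³}, where r(x) is the chance that one dose arm is significant given x.

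| Common response rate | Any false rejection, n=40 | n=50 | False benefit, n=40 | n=50 |
|---|---|---|---|---|
| 3% | 4.9% | 7.2% | – | – |
| 4% | 8.3% | 10.0% | – | – |
| 6% | 12.9% | 11.1% | 6.5% | 5.2% |
| 10% | 14.4% | 12.6% | 6.8% | 6.2% |

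Over rates of 5% to 20% the overall error runs from 11.0% to 14.5%. Below about 5% it drops quickly, so 12.5% is a large-sample figure and not a constant of the design.

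**3. Price of familywise control.** Hochberg on the same three p-values, 40 per arm, 6% placebo, 33% on each active dose (exact):

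| Doses that work | Overall error | Power per working dose | Unadjusted power |
|---|---|---|---|
| 0 | 2.0% | – | – |
| 1 | 2.9% | 78.9% | 90.4% |
| 2 | 4.0% | 82.7% | 90.4% |
| 3 | – | 87.8% | 90.4% |

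The largest loss is 90.4 − 78.9 = 11.5 points. Power to find at least one dose when all three work goes from 98.8% to 95.7%. A single-step Dunnett-type level (0.0188 per test) gives 81.7% per dose. Restoring 90% per dose under Hochberg takes 43 evaluable per arm if all doses work and 52 if only one does. At 20% dropout that is 43/0.8 ≈ 54 or 52/0.8 = 65 randomized per arm, against 50 planned.

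**4. Set the hypotheses side by side.** Section 10.1 of the SAP has an unindexed null, but its next paragraph compares each dose group with placebo. In Protocol section 4, the first clinical hypothesis (PASI 75) is generic, the second lists the three doses separately against placebo, and the third compares doses. Protocol section 5.5 discusses expected effects dose by dose. The consistent reading is that the active rate stands for each dose group in turn.

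**The case for a change.** The strongest case for a change is that declaring the approach costs only a few sentences and is worth most before unblinding. Split results would not be rare: with all three doses at the planned effect and 40 per arm, exactly one or two of the three tests reach p≤0.05 in about 20% of trials. The plan has no trial-level rule for those, and its analysis sections never call the p-values nominal.

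The facts stand. The null is loosely written, no adjustment exists and the overall error exceeds 5% at the planned placebo rate. The consequence does not follow. In a dose-ranging trial each dose gets its own answer against placebo, so a split result is a result about doses; a single pass/fail rule is a preference. The sample-size sections already show that the 5% is per comparison. A sentence declaring this would alter no test, level, sample size or result. The one proposal that would alter something, familywise control, gives up part of the stated 90% power for a standard the documents never adopt. A statistician could reasonably choose it, but leaving it out is not an error.

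**Conclusion.** No change to the plan is called for. The design and the analysis agree: three dose-placebo comparisons, each at two-sided 5%, each with 90% power at 40 evaluable per arm. No stated error rate or power is wrong. The unindexed null is a notational gap that an analyst fills sensibly by writing it once per dose and reporting the three p-values as unadjusted.

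The multiplicity is real but bounded. If all three doses are inert, at least one false rejection occurs about 12.5% of the time asymptotically and 11–13% exactly at a 6% response rate, less when the rate is under about 5%. False benefit is 5.2–6.5% exactly at 6%, against a nominal 2.5% per dose. Accepting that in Phase 2b, rather than losing 2.6 points (90.4 − 87.8) to 11.5 points of power per dose under Hochberg, is a fair trade-off.

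This rests on the uncorrected chi-square, the planning rates of 6% and 33%, equal arms, and results being read dose by dose. It would not carry over if the sponsor claimed a familywise 5% for the trial as a whole.
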